17.1.2 Physical Examinations

A complete physical examination, including a standard neurological examination should be completed at Screening and will include, at a minimum: the general appearance of the participant, height, weight, and examination of the skin, eyes, ears, nose, throat, lungs, heart, abdomen, extremities, musculoskeletal system, lymphatic system, and nervous system. Investigators should pay special attention to clinical signs related to previous serious illnesses and new or worsening abnormalities may qualify as AEs.

Symptom-directed physical exams are done thereafter at the visits indicated in the SoA, including the SFU visit (Section 10.2).

17.1.3 Vital Signs

Vital signs will be performed at timepoints specified in the SoA (Section 10.2)

Changes from baseline abnormalities should be recorded in participant notes. New or worsened clinically significant abnormalities should be recorded as AEs on the Adverse Event eCRF.

Pulse rate and blood pressure

Blood pressure and pulse/heart rate measurements will be assessed with a completely automated device. Manual techniques will be used only if an automated device is not available.

Blood pressure and pulse measurements should be preceded by at least 10 minutes of rest for the participant in a quiet setting.

Pulse rate and blood pressure measurement timepoints are:

- Screening
- Cycle 1 (Weeks 1 to 3) :
 - Predose (up to 2 hours prior to infusion)

- 1 hour after the start of the infusion (\pm 10 mins)
- At the end of the infusion (up to 10 minutes post dose)
- 4 hours after the start of the infusion (\pm 30 minutes)
- 6 hours after the start of the infusion (\pm 30 minutes)
- From Cycle 1, Week 4 onwards:
 - Predose (up to 30 minutes prior to infusion)
 - At the end of the infusion (up to 30 minutes post dose) on each dosing day
- 30-Day SFU

Body temperature

Body temperature will be measured in degrees Celsius at the following timepoints:

- Predose (up to 2 hours prior to all infusions)

Weight

Weight will be measured in kilograms at the following times:

- Screening,
- Cycle 1 (Weeks 1-3) (predose)
- Cycle 1 Week 4 onwards, of each cycle predose
- 30-Day SFU

17.1.4 WHO/ECOG Performance Status

ECOG performance status will be assessed at the following times (see Section 10.2):

- Screening
- Cycle 1 through Cycle 8:
 - Predose each dose of AZD4573
- Cycles 9+, Day 1 of each cycle:
 - Predose each dose of AZD4573
- 30-day SFU

Performance status should be measured using the ECOG Performance Status Scale ([Table 15](#)). It is recommended, where possible, that a participant's performance status be assessed by the same person throughout the study.

Table 15 ECOG Performance Status Scale

Grade	Description
0	Fully active, able to carry on all pre-disease performance without restriction
1	Restricted in physically strenuous activity but ambulatory and able to carry out work of a light or sedentary nature, eg, light housework, office work
2	Ambulatory and capable of all selfcare but unable to carry out any work activities; up and about more than 50% of waking hours
3	Capable of only limited selfcare; confined to bed or chair more than 50% of waking hours
4	Completely disabled; cannot carry on any selfcare; totally confined to bed or chair
5	Dead

17.1.5 B Symptoms

Information on B symptoms (eg, unintentional weight loss, fevers, and night sweats) will be collected at the following times ([Section 10.2](#)).

- Screening
- Cycle 1 through Cycle 8:
 - Predose AZD4573
- Cycle 9+, Day 1 of each cycle:
 - Predose AZD4573
- 30-day SFU

17.1.6 Clinical Safety Laboratory Assessments

For all participants, results of safety laboratory testing (haematology and clinical chemistry at a minimum) must be available within 72 hours prior to dosing and must be reviewed by the Investigator prior to administration of AZD4573 (all cohorts). If clinically indicated, additional clinical laboratory tests and evaluations may be performed by the Investigator (eg, additional haematology/clinical chemistry panels, TLS parameters, liver enzyme tests); these need to be entered into the eCRF.

This study will use local laboratories.

The following laboratory variables will be measured:

Haematology: complete blood count (CBC) with automated and/or manual differential including, but not limited to, white blood cell count, haemoglobin, haematocrit, platelet count, ANC, and absolute lymphocyte count (ALC), and blast cells. Haematology should be evaluated before dosing while participants are receiving treatment.

Haematology samples will be collected at the following timepoints:

- Screening
- Cycles 1, 2, and 3
 - Predose AZD4573 (within 72h prior to infusion)
 - 24 hours after the start of the infusion
- Cycles 4+
 - Predose AZD4573 (within 72 hours prior to infusion)
 - If clinically indicated, 24 hours after the start of the infusion
- 30-Day SFU

The Investigator may take additional, unscheduled samples throughout the study if deemed clinically warranted and these need to be entered into the eCRF.

Haematology tests do not need to be repeated before first dose if the first-dose visit is within 3 days of the Screening sample.

Clinical Chemistry: albumin, chloride, bicarbonate, calcium total, magnesium, phosphorous, glucose (fasting preferred), CK, ALP, ALT, ammonia (where available at local institution; to be tested every 2 weeks), AST, urea, , cholesterol, C-reactive protein, creatinine, Factor V (where available at local institution), GGT, lactate dehydrogenase (LDH), phosphate, potassium, sodium, triglycerides, total bilirubin, direct and indirect bilirubin, total protein, uric acid.

Clinical chemistry samples will be collected at the following timepoints:

- Screening
- Cycles 1, 2, and 3
 - Predose AZD4573 (within 72 hours prior to infusion)
 - 24 hours after the start of the infusion
- Cycles 4+

- Predose AZD4573 (within 72 hours prior to infusion)
- If clinically indicated, 24-hour after the start of the infusion
- 30-Day SFU

The Investigator may take additional, unscheduled samples throughout the study if deemed clinically warranted and these need to be entered into the eCRF.

Clinical chemistry and haematology tests do not need to be repeated before first dose if the first-dose visit is within 3 days of the Screening sample.

In addition, GLDH and CPK will be measured at Screening for all participants. If GLDH cannot be performed locally, LDH will be analysed locally and a serum sample must be collected for central retrospective GLDH analysis, which will be performed as applicable. Refer to the Laboratory Manual for details.

Coagulation testing includes aPTT (partial thromboplastin time)/PT (prothrombin time), INR, D-dimer (where available at institution), and fibrinogen.

Samples for coagulation testing will be collected at the following timepoints:

- Screening
- Cycles 1, 2, and 3
 - Predose AZD4573 (within 72 hours prior to infusion)
 - 24 hours after the start of the infusion
- Cycles 4 through 8
 - Predose AZD4573 (within 72 hours prior to infusion)
 - If clinically indicated, 24-hour after the start of the infusion
- Cycles 9+ on Day 1 of each cycle
 - Predose AZD4573 (within 72 hours prior to infusion)
- 30-Day SFU

The Investigator may take additional, unscheduled samples throughout the study if deemed clinically warranted and these need to be entered into the eCRF.

Urinalysis: pH, ketones, specific gravity, bilirubin, protein, blood, and glucose. Urine samples should be collected at the following timepoints:

- Screening

- Cycles 1 through 8
 - Predose AZD4573 (within 72 hours prior to infusion)
 - Within approximately 2 hours after the end of the infusion
- Cycles 9+ on Day 1 of each Cycle
 - Predose AZD4573 (within approximately 72 hours prior to infusion)
 - Within approximately 2 hours after the end of the infusion
- 30-Day SFU

Cardiac troponin I or troponin T measurements are required at the timepoints below. Either a troponin I or troponin T assay can be used per SoC at the respective hospital. If the hospital has both a SoC troponin I and troponin T assay available, the investigator should use only one consistently for the duration of the study.

- Screening
- Cycle 1, Weeks 1 through 5
 - Predose (within 72 hours prior to infusion)
 - 24 hours post start of the infusion
- Cycles 2+ on Day 1 of each cycle
 - Predose (within 72 hours prior to infusion)
- 30-Day SFU

Electrolyte panel: calcium, magnesium, potassium.

If an unscheduled ECG is done at any time, then an electrolyte panel (ie, calcium, magnesium, potassium), and troponin must be done to coincide with the ECG testing.

Supra-renal glands: T4, cortisol, adrenocorticotropic hormone (ACTH) and thyroid-stimulating hormone (TSH) should be measured at the following timepoints:

- Screening
- Cycle 2 Day 1
 - Predose AZD4573 (within 72 hours prior to infusion)
- 30-Day SFU

Pancreas: Lipase and amylase measurements are required at the following timepoints:

- Screening
- Cycles 1 through Cycle 8
 - Predose AZD4573 (within 72 hours prior to infusion)
- Cycles 9+ on Day 1 of each Cycle
 - Predose AZD4573 (within 72 hours prior to infusion)
- 30-Day SFU

Lipase/amylase tests do not need to be repeated before first dose if the first-dose visit is within 3 days of the Screening sample.

TLS monitoring will include: potassium, calcium, phosphate, uric acid, and creatinine.

TLS monitoring will be performed at the following timepoints:

- Cycle 1, Weeks 1 through 3
 - Predose AZD4573
 - 6 hours (\pm 30 minutes) after the start of the infusion
 - 24 hours (\pm 1 hour) after the start of the infusion (and prior to acalabrutinib dosing)

Participants showing signs of clinical or laboratory TLS at 6 hours after the start of the infusion must be admitted for in-patient TLS monitoring for a minimum of 24 hours after the start of the infusion and monitored every 4 to 6 hours during this time (or more frequently if clinically indicated).

For each TLS monitoring timepoint, a TLS Monitoring page in the eCRF is to be filled out.

Hepatitis serology will be conducted at Screening. Hepatitis serology must include hepatitis B surface antigen (HbsAg), hepatitis B surface antibody (anti-HBs), anti-HBc, and hepatitis C (HCV) antibody. Participants who are anti-HBc positive, or have a known history of hepatitis B virus (HBV) infection, should be monitored every 3 months with a quantitative PCR test for HBV DNA (Section 17.1.10.4). In addition, any participants testing positive for any hepatitis serology must have PCR testing for verification purposes.

Pregnancy: a sample for a pregnancy test will be collected from all female participants of childbearing potential at:

- Screening (serum)
- Cycle 1, Week 1

- Predose
- Cycles 2+ once every 21 days (\pm 7 days) prior to initiating a new cycle
- 30-day SFU visit

Pregnancy tests after Screening may be serum or urine. Urine β -hCG and quantitative serum β -hCG tests are permitted. If a urine β -hCG test is positive or indeterminate, quantitative serum β -hCG will be performed for confirmation. Additional testing may be performed at Investigator discretion, for example in the event of suspected contraception failure.

Liver chemistry tests: For any participant on study who experiences elevated ALT /AST $\geq 3 \times$ ULN and/or elevated total bilirubin $\geq 2 \times$ ULN: repeated liver chemistry tests (INR, fibrinogen, D-dimer [where available at institution], ALP, ALT, AST, GLDH, CPK, total bilirubin, direct bilirubin, indirect bilirubin) are required at 48 hours (-2/+12 hours) and 96 hours (-2/+12 hours) after the start of the infusion and every 48 hours (-2/+12 hours) thereafter until resolution of the event. If an event is not resolved within 96 hours the medical monitor shall be contacted. If GLDH cannot be performed locally, LDH will be analysed locally and a serum sample must be collected for central retrospective GLDH analysis. Refer to the Laboratory Manual for details.

During the course of the study the Investigator will remain vigilant for increases in liver biochemistry. The Investigator is responsible for determining whether a participant meets PHL criteria at any point during the study. The Investigator participates, together with the Sponsor, in review and assessment of these cases. Hy's Law (HL) criteria are met if there is no alternative explanation for the elevations in transaminases and total bilirubin levels.

If an unscheduled ECG is done at any time: troponin and an electrolyte panel* must be done to coincide with the ECG testing.

* can include: sodium, calcium, potassium, chloride, phosphate, magnesium.

If a participant is assessed as meeting PHL criteria, please refer to [Appendix E](#).

CMV: All subjects will have CMV testing at Screening including serology testing for CMV immunoglobulin (Ig)G and CMV IgM and CMV DNA PCR testing. Subjects must have a negative result for CMV DNA PCR such that CMV DNA is not detected by PCR at Screening, to be eligible for the study. The Screening CMV serologies will be advisory only, to guide investigators in assessing the risk of new infection or reactivation of CMV while on study.

17.1.7 Other Safety Assessments

Monitoring for TLS per the SoA (Section 10.2) and prophylaxis for TLS are outlined in detail in Section 17.1.10.10.

Blood samples for **CCI** will be collected per the SoA (Section 10.2) and as outlined in Section 17.9.6.

Additional safety assessment requirements include:

- **Echocardiograms (ECHOs):** In addition to Screening, an ECHO should be done within 14 days after an abnormal ECG finding (eg, T-wave inversion/flattening) or as soon as possible when clinically indicated. If an ECHO cannot be taken, a multigated acquisition (MUGA) scan to assess left ventricular ejection fraction (LVEF) will be done. In case of any T-wave abnormality, the ECHO (or MUGA) should be repeated at the 30-day SFU visit to address the question of recovery, during the off-treatment period.
- **CD4, CD8, CD19, CD16/NK** cell count and serum immunoglobulins (IgA, IgM, IgG)
 - Screening
 - Day 1 of Cycles 2, 4, 7, 9, 13, 16, 19
 - Predose
 - Every 6 months thereafter (predose)
 - 30-Day SFU

17.1.8 Electrocardiograms (ECGs)

Twelve-lead ECGs will be obtained after the participant has been resting semi-supine for at least 10 minutes before the times indicated. All ECGs should be recorded with the participant in the same physical position where possible.

If an abnormal ECG finding at Screening or baseline is considered to be clinically significant by the Investigator, it should be reported as a concurrent condition. If a clinically significant abnormal ECG finding occurs on study, contact the Medical Monitor.

Single ECGs will be collected for local and central analysis at the following timepoints:

- Screening
- Cycle 1, Weeks 1 through 5 and Cycle 2, Day 1:
 - Predose (at the day of infusion prior to infusion)
 - End of infusion (within 30 minutes of end of infusion)
- Cycles 3+, Day 1 of each cycle:

- Within 30 minutes after the end of infusion
- 30-Day SFU

Any abnormal finding in the ECG tracing will be evaluated by the Investigator and will be specifically documented and registered in the eCRF. Throughout the study, clinically relevant new findings or worsening of a pre-existing finding in the ECGs (parameters or abnormal findings in the tracing) must be considered an AE and must be recorded in the AE CRF form.

If an unscheduled ECG is done at any time, then an electrolyte panel (ie, calcium, magnesium, potassium) and troponin I/troponin T must be done to coincide with the ECG testing. Note: either a troponin I or troponin T assay can be used per SoC at the respective hospital. If the hospital has both a SoC troponin I and troponin T assay available, the investigator shall use only one consistently for the duration of the study.

17.1.9 Follow-up

17.1.9.1 30-day SFU Visit

An SFU visit will be performed 30 (\pm 7) days from the time that both study drugs are permanently discontinued (see the SoA [Section 10.2]). Tumour assessments will be repeated at this visit if they have not been performed within 9 weeks if the participant discontinued before Week 53, or 12 weeks if the participant discontinued after Week 53.

17.1.9.2 Long-term Follow-up Visits

Participants who discontinue both study drugs before documented disease progression will be followed according to SoC until documented disease progression or the start of new anti-cancer therapy. Disease progression or start of new anti-cancer therapy will be captured in the eCRF. During this period, only information on any SAEs considered related to IP or study procedures will be collected. If a participant is unable to attend site for this visit, the long-term follow-up may be performed via phone call. Long-term follow-up visits will cease at disease progression or start of a new anti-cancer therapy, whichever comes first. The long-term follow-up will not apply to participants who withdraw consent or are lost to follow-up.

17.1.9.3 Survival Follow-up

All participants will be followed for survival until death, loss to follow-up, AstraZeneca closes the study, or withdrawal of consent, whichever occurs first. Participants will be followed for survival by telephone calls or clinic visits approximately every 3 months. Site personnel will attempt to collect the vital status of the participant within legal and ethical boundaries for all participants who received investigational product. Public sources may be searched for vital status information. If vital status is determined as deceased, this will be documented and the participant will not be considered lost to follow-up. Sponsor personnel will not be involved in

any attempts to collect vital status information. During this period, information will be collected in the eCRF on survival status and any new anti-cancer therapies, and on any SAEs considered related to study drug(s) or study procedures.

The follow-up calls/clinic visits for survival should occur every three months, starting 3 months after end of treatment/discontinuation (ie, 3/6/9/12 months after treatment). In case a shorter/longer interval between two follow-up calls occurs the frequency should return to the multiple of 3 months after treatment (eg, 3/6/9/12 months after treatment and so on).

In preparation for an analysis, survival calls will be made in the week following the data-cut-off for the analysis.

17.1.10 Prevention and Management of Safety Concerns for AZD4573 in Combination with Acalabrutinib

This section provides recommendations for treatment of potential toxicities associated with acalabrutinib, or the combination of AZD4573 with acalabrutinib, and guidance about modifying the doses of acalabrutinib and AZD4573 due to those toxicities. For complete safety information refer to [CCI](#) and [Calquence United States Prescribing Information](#).

Generally, Grade 1 or 2 non-haematological and/or haematological toxicities do not require AZD4573 or acalabrutinib dose reductions and should be managed as medically indicated (with or without short dose interruptions) by the treating physician. Grade 3 and 4 toxicities require dose modifications, temporary treatment interruptions, or discontinuation of AZD4573 and acalabrutinib. These are described in [Table 13](#) and [Table 14](#).

17.1.10.1 Headache

Headache is an identified risk for acalabrutinib. Participants with headache should be managed per institutional guidelines with supportive care and diagnostic evaluations as clinically indicated.

Note: encouraging adequate hydration for participants experiencing headaches has anecdotally been helpful in some cases.

17.1.10.2 Diarrhoea

Diarrhoea is an identified risk for AZD4573 and acalabrutinib. Participants with diarrhoea during therapy should be managed per institutional guidelines with maximal supportive care and diagnostic evaluations as clinically indicated. After excluding infectious aetiologies, symptomatic management should be considered. Participants experiencing prolonged or severe diarrhoea should be closely monitored and managed as appropriate if dehydration

and/or electrolyte abnormalities are observed. Participants should be made aware of the risk of possible overlapping toxicities of diarrhoea while receiving combination study treatments.

Prophylaxis for diarrhoea with atropine is strongly recommended for all participants enrolled into the study as an anti-cholinergic drug, administered at 0.5 mg subcutaneously 15 to 30 minutes prior to all scheduled AZD4573 infusions. In the event of multiple episodes of diarrhoea despite atropine prophylaxis, one additional atropine dose may be considered and administered as outlined above.

In addition, in the event of diarrhoea, participants should remain fully hydrated with additional IV fluids.

17.1.10.3 Nausea and Vomiting

Nausea and/or vomiting are identified risks for AZD4573 and acalabrutinib. Participants with nausea and/or vomiting during therapy should be managed per institutional guidelines with maximal supportive care and diagnostic evaluations as clinically indicated. Participants experiencing prolonged or severe vomiting should be closely monitored and managed as appropriate if dehydration and/or electrolyte abnormalities are observed. Participants should be made aware of the risk of possible overlapping toxicities of nausea and vomiting while receiving combination study treatments.

Nausea and vomiting are considered important identified risks for AZD4573. Events of nausea and vomiting have been observed in approximately half of all participants dosed with AZD4573 and have occurred at all dose levels tested to date (except 3 mg). Prophylaxis with a 5-HT3 antagonist (eg, ondansetron \pm dexamethasone) has been implemented in the Phase I study (D8230C00001) to help alleviate this toxicity.

Therefore, prophylaxis for nausea and vomiting is recommended as follows: administer dexamethasone 8 mg (IV administration preferable but orally also permitted) plus a 5-HT3 antagonist (e.g. ondansetron initially 8 mg to be taken before treatment, then 8 mg every 12 hours for up to 3 days) as anti-emetics for all participants, approximately 30 to 60 minutes prior to all scheduled AZD4573 infusions. Additional doses of dexamethasone 8 mg may be administered if deemed clinically warranted. In addition, in the event of vomiting, participants should remain fully hydrated with additional fluids. Participants experiencing prolonged or severe nausea and vomiting should be closely monitored and managed as appropriate if dehydration and/or electrolyte abnormalities are observed.

17.1.10.4 Hepatitis B Reactivation

Serious or life-threatening reactivation of viral hepatitis have been reported in participants treated with acalabrutinib. Therefore, participants who are anti-HBC positive, or have a known history of HBV infection, should be monitored every 3 months with a quantitative PCR test

for HBV DNA. Monitoring should continue until 12 months after last dose of acalabrutinib. Any participant with a rising viral load (above lower limit of detection) should discontinue acalabrutinib and have antiviral therapy instituted and a consultation with a physician with expertise in managing hepatitis B. Insufficient data exist regarding the safety of resuming acalabrutinib in participants who develop HBV reactivation.

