4.5 End of Study Definition

The end of module is defined as the last scheduled visit or contact of the last participant enrolled in the module.

The overall end of the study is defined as the date of the last visit of the last participant. In the event any participant remains on treatment following the end of the data collection for the primary analysis, the last visit of the study will be the date when the last participant permanently discontinued treatment with all investigational products. However, the database will be closed following end of data collection, and participants remaining on treatment will only be followed for SAEs. In all other aspects, the participant will receive SoC as per local practice.

Individual participants will normally be considered to have completed the study if they have had a 30-Day Safety Follow-up visit performed, or if the treating site has confirmed the SFU visit will not be performed. For participants continuing treatment after the data cut-off for the primary analysis the last visit of the study will be the date when the last participant permanently discontinued treatment with all investigational products.

Details of planned data analyses are provided in each of the study modules. The results from each module will be reported to Regulatory Authorities within one year of the end of the module.

Details on dissemination of clinical data are contained in Appendix [A 6](#).

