6.13 Intervention After the End of the Study

After the data cut-off for the primary analysis, the clinical study database will be closed to the entry of new data. However, patients still receiving AZD4573 at that time will be able to continue receiving study treatment (in accordance with guidance in this protocol and the IB) if, in the opinion of the Investigator, they are still deriving clinical benefit.

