- ^o All participants will receive TLS prophylaxis during the intra-patient ramp up and be monitored for TLS during the first 24 hours post start of dose; this requirement will continue until they have received at least one AZD4573 dose at the target dose level (i.e., for at least the first 3 AZD4573 once-weekly doses). TLS monitoring will be performed at the following timepoints: predose AZD4573, 6 h after the start of the infusion, and 24 h (\pm 1 h) after the start of the infusion. Participants showing signs of clinical or laboratory TLS at 6 h after start of infusion must be admitted for in-patient TLS monitoring for a minimum of 24 h after the start of the infusion and monitored every 4 to 6 h during this time (or more frequently if clinically indicated). For each TLS monitoring timepoint, a TLS Monitoring page in the eCRF is to be filled out. Fluid balance must be monitored according to local institutional standards.
- ^p Urine samples will be collected at the following timepoints: Screening, Cycles 1-8, predose AZD4573 (within 72 hours prior to infusion) and within approximately 2 hours after the end of infusion, Cycles 9+ on Day 1 of each cycle, predose AZD4573 and within approximately 2 hours after the end of infusion, and at the 30-day SFU.
- ^q Pregnancy test to be performed at Screening (serum) and predose (serum or urine) on Cycle 1, Week 1, then once every 21 days (\pm 7 days) prior to initiating a new cycle and at the 30-day SFU visit. Additional testing may be performed at Investigator discretion (eg, in the event of suspected contraception failure).
- ^r Lipase and amylase should be evaluated at Screening, Cycles 1-8 predose AZD4573 (within 72 hours prior to infusion), Cycles 9+, predose AZD4573 (within 72 hours prior to infusion) on Day 1 of each cycle, and at the 30-day SFU visit.
- ^s In addition to hepatitis serology as specified, participants who are anti-HBc positive, or have a known history of HBV infection, should be monitored every 3 months with a quantitative PCR test for HBV DNA. In addition, any participants testing positive for any hepatitis serology must have PCR testing for verification purposes.
- ^t CD4, CD8, CD19, CD16/NK and serum immunoglobulins (IgA, IgM, IgG) will be drawn at Screening, Day 1 (predose) of Cycles 2, 4, 7, 9, 13, 16, 19 and every 6 months thereafter (predose), and at the 30-day SFU.

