15.7 Duration of Therapy

Treatment with AZD4573 and acalabrutinib, in Part A and Part B, may be continued until disease progression, an unacceptable drug-related toxicity occurs as defined in the protocol, or the participant withdraws or is withdrawn from the study for other reasons.

For both Part A and Part B, Cycle 1 comprises 5 weeks with a ramp-up period. Cycle lengths are 3 weeks from Cycle 2 onwards. For information on dosing schemes and cycle lengths, see [Figure 5](#) and [Table 8](#).

Any participant who is still on treatment and is receiving clinical benefit from the IP by the end of data collection for the primary analysis will be allowed to continue study treatment. Such participants will continue to be monitored for all SAEs up to 30 days after the last dose of IP. However, the database will be closed following end of data collection, and participants remaining on treatment will only be followed for SAEs (paper report). If a participant is continuing study treatment after the end of data collection, the Investigator should refer to the current IB for treatment guidance and safety surveillance.

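### For participants treated beyond the end of data collection, the SAE-only follow-up in Sections 4.5 and 15.7 conflicts with the HBV DNA monitoring set in Section 17.1.10.4

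*Protocol*

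**What the plan says.** **The monitoring rule.** Section 17.1.10.4 (Module 1) describes viral hepatitis reactivation under acalabrutinib as serious or life-threatening. It sets a quantitative HBV DNA PCR every 3 months for at-risk participants and gives the stopping point: "Monitoring should continue until 12 months after last dose of acalabrutinib". A rising viral load calls for stopping acalabrutinib, antiviral therapy and a specialist consultation. Section 14.2 admits anti-HBc-positive participants who are surface-antigen and PCR negative, so at-risk participants can be in the trial.

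**Where it is repeated.** The hepatitis footnotes of Tables 4 and 5 (Section 10.2) and Section 17.1.6 say that these participants "should be monitored every 3 months with a quantitative PCR test for HBV DNA", without the 12-month end point. The hepatitis row of the schedule and Section 17.1.6 both refer to Section 17.1.10.4.

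**Continued treatment after data collection.** Section 4.5: "However, the database will be closed following end of data collection, and participants remaining on treatment will only be followed for SAEs"; its next sentence leaves all other care to local practice. Section 15.7: "Such participants will continue to be monitored for all SAEs up to 30 days after the last dose of IP". It repeats the SAE-only limit and names the current IB as the source for treatment guidance and safety surveillance. Section 6.13 lets these participants "continue receiving study treatment (in accordance with guidance in this protocol and the IB".

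**Post-treatment contacts.** The safety follow-up visit is at 30 (±7) days (Section 17.1.9.1). Section 17.1.9.2: "Long-term follow-up visits will cease at disease progression or start of a new anti-cancer therapy, whichever comes first". Survival contacts (Section 17.1.9.3) fall at months 3, 6, 9 and 12 after treatment, may be telephone calls, and name no laboratory test.

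**The concern.** This amendment has, as part of its main purpose, to let participants who still benefit continue treatment after the primary analysis data are collected. Its text for that group was not reconciled with the HBV rule. One section sets a dated monitoring schedule for a life-threatening risk. Two others say that the same people are followed only for SAEs and otherwise fall under local practice or the IB.

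What is at stake is patient safety. SAE follow-up picks up a reactivation once it is clinically serious; the PCR is there to find rising virus before that. If the test is dropped while acalabrutinib continues, the first response in Section 17.1.10.4, stopping the drug, loses its trigger. If it is dropped after treatment, antiviral therapy and specialist referral may come late.

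**Working it through.** The plan gives no figure to reproduce. The check sets the sections side by side and counts tests.

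**Which instruction governs a continuing at-risk participant?**

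| Section | On continued treatment | After the last dose |
|---|---|---|
| 17.1.10.4 | PCR every 3 months | PCR every 3 months to month 12 |
| 4.5 | SAEs only; otherwise local standard of care | no HBV provision |
| 15.7 | SAEs only, on paper; surveillance per IB | SAEs to 30 days; no HBV provision |
| 6.13 | protocol and IB guidance apply | not addressed |

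Sections 15.7 and 17.1.10.4 both belong to Module 1, so a rule that the module overrides the core could not decide between them. The precedence rule in Sections 5.1 and 14 concerns eligibility criteria in any case. Nothing in the text ranks one row above another.

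**How many tests are exposed?** Assume that both drugs stop on day 0 and that 12 months is 365 days.

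- Post-treatment tests due: 12 months / 3 months = 4, at about days 91, 183, 274 and 365.
- Safety follow-up visit: 30 ± 7 = days 23 to 37, before the first of these.
- Tests due during continued treatment of *t* months: about *t*/3. The length of continued treatment is not known.
- Post-treatment tests missed per at-risk participant: 0 if the site follows Section 17.1.10.4, up to 4 if it follows only Sections 4.5 and 15.7.

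**Do later contacts catch the tests?** Survival contacts coincide with months 3, 6, 9 and 12 but can be made by telephone, and survival follow-up ends when the sponsor closes the study. Section 13.4 counts a continuing participant as having completed Module 1 on the date AZD4573 is permanently discontinued. The 12-month tail can therefore run past every scheduled contact.

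**The case against.** The strongest reply is that nothing forbids the test. In both Sections 4.5 and 15.7 the SAE-only wording shares a sentence with database closure, and Section 15.7 mentions paper reporting, so it can be read as a rule about data capture. Section 15.7 does not abolish surveillance but assigns it to the IB, which is not among the documents here. Section 17.1.10 introduces itself as recommendations. Recruitment has stopped, and in the ibrutinib experience cited in Section 13.2.1 median overall survival was 6.41 months, so four tests is a ceiling that some participants will not reach.

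Much of this stands and limits the size of the point. It does not remove the conflict. The sentence in Section 4.5 about all other aspects describes care, not data entry. Local practice or an IB replaces the protocol's own schedule with something that may or may not contain it.

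Three stronger readings are tempting, and the documents do not support them.

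- A reader might infer that the schedule tables contradict Section 17.1.10.4 because their footnotes omit the end point. They do not: the hepatitis row and Section 17.1.6 lead to that section, so only a detail is missing.
- A reader might infer that the schedule lists none of the post-treatment tests. The prose of Section 17.1.9 names none, but the hepatitis cell in Tables 4 and 5 that points to the footnote appears to be merged, and its span cannot be recovered from the text at hand.
- A reader might subtract the 30-day SAE window from the 12 months and call the remainder lost monitoring. That compares a reporting window with a clinical instruction; a shorter reporting period does not cancel a longer duty of care.

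**Conclusion.** The point holds for participants who continue treatment after data collection. Sections 4.5 and 15.7 conflict with Section 17.1.10.4, Section 6.13 supports Section 17.1.10.4, and a site has two defensible readings. One of them ends HBV DNA testing on and after treatment.

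The loss is possible, not shown. It is 0 to 4 post-treatment tests per at-risk participant, plus any due during continued treatment. The count assumes that both drugs stop together and that the participant survives the 12 months. The number of anti-HBc-positive or HBV-history participants who continue is not given and may be zero, and the content of the IB is unknown. Detection is what is exposed, not reporting: all SAEs stay reportable on continued treatment and to 30 days after it, and Section 8.2.1 keeps later SAEs with a suspected causal link reportable. Sample size, error rates and efficacy analyses are untouched. The change should be made because the risk is serious and the remedy is small.

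**What to change.** 1. In Sections 4.5 and 15.7, add a sentence: for participants who are anti-HBc positive or have a history of HBV infection, SAE-only follow-up and closure of the database do not end HBV DNA monitoring under Section 17.1.10.4. This must stand alone, because survival contacts may no longer take place for this group.
2. In Section 17.1.9.3, note that for these participants the month 3, 6, 9 and 12 contact should be accompanied by the PCR that Section 17.1.10.4 already sets, with a local blood draw acceptable.
3. Optionally, repeat the 12-month end point in the hepatitis footnotes of Tables 4 and 5.

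The cost is one sentence in each of three sections and, for a few participants, a local blood draw in place of a telephone call alone. No test is added beyond those in Section 17.1.10.4, and no analysis changes.
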